Participants who self-report abstinence will be mailed a prepaid envelope, instructions for providing the cotinine sample, and a saliva cotinine kit. Research staff will contact participants by phone to ensure the arrival of packet, review the contents of the packet, and answer any questions participants may have about collecting a saliva specimen. Although cotinine cannot comprehensively validate the various abstinence definitions and timeframes, the most comprehensive review on biochemical validation concluded that misreporting is typically very low (~2%), and that adjustment for misreporting almost never influences analyses regarding relative treatment efficacy.¹⁰⁶ As such, our biochemical validation procedures are well justified both scientifically and practically.

PSYCHOLOGICAL DISTRESS ASSESSMENT AND MANAGEMENT PLAN

If a participant: 1) states that she is thinking about harming herself or others, or 2) uses actions or words to lead us to believe that she may be in eminent danger or in danger of harming another person, research staff will execute our standard crisis procedures. These procedures are described in detail in Appendix H. Once the plan is executed, a trained counselor will assess the participant using the "Crisis Assessment" (Appendix I). Participants will also be encouraged to follow ups with a mental health professional of their choice. Our team will have extensive interactions with participants throughout the course of the study. Therefore, our plan is appropriate for our target population.

STATISTICAL CONSIDERATIONS

Data Analysis Approach. The primary outcome is abstinence from smoking at the 18-month assessment. To test the treatment effect at 18 months, we will conduct logistic regression analysis with abstinence as the outcome variable, and treatment (a two-level categorical variable) as the predictor, adjusting for covariates, specifically, factors used in the minimization procedures (race/ethnicity, language, age, education, income, cigarettes/day, cervical cancer stage, and time since diagnosis). Interactions between treatment and specific covariates of interest may be included and tested for exploratory purposes.

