Because the primary and secondary outcomes and mechanisms include repeated measurements that are correlated within subjects, our data analytic approach will also utilize generalized linear mixed model regression (GLMM)^{107,108} to analyze the effects of MAPS across the 3, 6, 12, and 18 month timepoints. For abstinence, we will assume a logit link and binomial variance function for the GLMM, and parameterize them with blocking on individual nested within treatment conditions. Treatment and time will be included, as well as their interaction, with adjustment for relevant covariates. The effects of interactions between treatment and specific covariates will also be examined. Similarly analyses will also be conducted to assess the MAPS effects on quit attempt and use of the quitline (both binary). To assess MAPS effects on continuous measures such as cigarettes per day and mechanisms, the GLMM analysis will be replaced by linear mixed model (LMM) analysis (i.e., a special case of the GLMM). Similarly, the logistic regression analysis for the 18-month assessment will be replaced by multiple linear regression. Normalizing transformations for continuous measures (such as cigarettes per day) will be applied as appropriate. Alternatively, Poisson GLMM or Poisson regression could be used to analyze the effect of MAPS on cigarettes per day. In addition to examining the effects of treatment on primary and secondary outcomes and mechanisms, we will also assess the mediation (indirect) effects of treatment on abstinence through the mechanisms (motivation, agency, stress/negative affect) using single and/or multiple mediator models.¹⁰⁹ With the primary outcome being abstinence at the 18-month assessment, potential mediators will be mechanisms measured at the previous time points (i.e., 3, 6, and 12 months), one at a time. A recommended approach to estimating and/or testing for the indirect effects for a binary outcome variable is via coefficient standardization in the *b* path (e.g., logistic regression), as appropriate, and bootstrapping.¹⁰⁹⁻¹¹¹ Appropriate covariates including mediators measured as baseline will be

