adjusted for in the *a* and *b*-path analyses. Mediators in the final mediator model will be selected using a backward selection approach.¹¹² We will also compute and compare proportions of mediated effects along with their standard errors across the single and multiple mediator models, as well as across time points where the mediators are measured.¹¹³ A larger proportion of the mediated effect in general suggests a larger mediation effect. Additional mediation analysis for repeated measures abstinence analyses will be conducted using a similar approach with both *a* and *b* paths involving repeated measures analysis, as applicable.¹¹³

Missing Data and Dropouts. It is anticipated that some individuals will drop out or be lost to follow-up, as is typical in smoking cessation treatment studies. Our primary analysis for examining abstinence at 18 months will utilize an intent-to-treat approach by coding missing abstinence data as smoking. However, we will also conduct sensitivity analyses by examining alternative approaches for handling missing data, including multiple imputation (under a missing at random assumption),^{114,115} and selection models (under an assumption of non-ignorable missingness, or missing not at random).^{114,116-118} In the multiple imputation approach, we will conduct analyses to examine whether participants who drop out of the study differ from those who do not, and include those covariates in our multiple imputation models, to mitigate the potential impact of non-ignorable missingness. Regardless of the approach used to handle missing data, it is unlikely that serious biases in estimation or considerable loss of efficiency in inference will result when the proportion of missing data low (e.g., not more than 10%; even more so when the missing data proportions are similar in MAPS and ST).

Overall, robust results based on both the primary and sensitivity analyses will strengthen our study findings.

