Power. Our power analysis is based primarily on the comparison of 18-month abstinence rates between MAPS and ST. Because an intent-to-treat approach will be used, power is calculated based on the full sample without attrition (N=300; 150 per group), given that individuals lost to follow-up will be treated as smoking). All power analyses assume a significance level of 0.05 and a two-sided test. Based on the *Guideline*,²⁰ we estimated that abstinence for ST would be approximately 10%. Using a chi-square test to examine the effect of treatment on abstinence at 18 months, a sample size of 300 (150 per group) will provide 80% power to detect an overall treatment effect that corresponds to abstinence rates of 10% and 21.9% in ST and MAPS respectively. Relative to examining abstinence over time, these calculations represent the worst case scenario. Table 2 presents detectable differences across a range of possible abstinence rates. Analyses conducted using GLMM will have greater power to detect the same average differences across time.

Table 2. Detectable differences in binary smoking outcomes with 80% power (abstinence, quit attempt)	
ST (n=150)	MAPS (n=150)
5.0%	14.60%
10.0%	21.90%
20.0%	34.40%
30.0%	45.70%
40.0%	56.20%

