Although the proposed mediation analyses for aim 2 are theoretically-grounded and hypothesis-driven (see Figure 1), they are quasi-exploratory in nature, and the sample size for this study was based on power to detect a significant difference for Aim 1. Nonetheless, power for the mediation analyses (Aim 2) has been calculated as follows. For the mechanism analyses (Aim 2), power is based on a conservative 25% attrition rate (N= 300; 112 per group). Because the mechanism variables are continuous, a sample size of 300 (112 per group at 18 months) will provide 80% power to detect an effect size of 0.376 standard deviation (SD) unit (difference in means between the ST and MAPS divided by common SD), using a two group t-test with a 0.05 two-sided significance level. Because we have excellent power to detect treatment effects on the primary outcome and mechanisms, as well as the effects of mechanisms on abstinence (with power generally greater using continuous predictors than binary predictors such as treatment group), we expect to have good power to detect mediation effects. We note, however, that the power calculated for analyses in Aim 2 should be considered in the context of inflated type 1 error due to multiple analyses and hypothesis tests (including the mediation analyses) being performed for this aim. We feel that this inflated type 1 error is acceptable given the quasi-exploratory nature of this aim. Nevertheless, future studies focusing on testing specified mediational models should be sufficiently powered using approaches of Fritz and MacKinnon¹¹⁹ or Thoemmes et al.¹²⁰, as appropriate.

Cost Effectiveness

Methods overview. Cost-effectiveness analyses (CEA) will compare the two interventions: ST and MAPS. The conventional CEA summarizes study findings in terms of the incremental cost-effectiveness ratio (ICER).^{121,122} The ICER, calculated as the difference in mean costs between the new and standard treatment divided by the difference in mean effectiveness between the new and standard treatment, estimates the additional resource consumption needed to achieve an increase in an additional unit of effectiveness. The ICER is then compared with a commonly cited or published threshold value associated with an intervention already found to be cost-effective to determine whether a new intervention is cost-effective.

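### The 18-month regression of each mechanism does not list that mechanism's baseline score as a covariate, and the mixed model leaves it open; naming it is a free, minor gain in precision.

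*Combined protocol and SAP*

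**What the plan says.** Under Statistical Considerations, Data Analysis Approach, the combined protocol and SAP plans three analyses that estimate the effect of MAPS on a mechanism.

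- **Mixed model.** The repeated-measures approach is meant "to analyze the effects of MAPS across the 3, 6, 12, and 18 month timepoints". For the mechanisms, "To assess MAPS effects on continuous measures such as cigarettes per day and mechanisms, the GLMM analysis will be replaced by linear mixed model". Treatment, time and their interaction enter, with adjustment for covariates called relevant but not listed.
- **18-month regression.** Multiple linear regression takes the place of the logistic model used for abstinence. The covariates given for that logistic model are the minimization factors, spelled out as "race/ethnicity, language, age, education, income, cigarettes/day, cervical cancer stage, and time since diagnosis".
- **Mediation a path.** The mechanism at month 3, 6 or 12, one at a time, is modelled on treatment. Here the plan does say that the mediator's baseline value is among the covariates, in both the a and the b path. A repeated-measures version by a similar approach is foreseen where applicable.

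Table 1 schedules all the motivation, agency and stress or affect instruments at baseline and at every follow-up. Under Power, the Aim 2 calculation is for 18 months: "power is based on a conservative 25% attrition rate (N= 300; 112 per group"), and this sample "will provide 80% power to detect an effect size of 0.376 standard deviation (SD) unit", "using a two group t-test with a 0.05 two-sided significance level".

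**The concern.** Psychological scales usually correlate with their own earlier value, and the mechanism scores are not minimization factors, so the allocation does not balance them. If a direct test of MAPS on a mechanism omits the baseline score, variation between women that the baseline would explain stays in the residual. The standard error is then larger than the collected data require, and a chance baseline difference between the arms is left uncorrected in that estimate.

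The plan treats its own continuous outcomes unevenly. Cigarettes per day has its baseline value on the covariate list because it is a minimization factor. The mechanisms have none, except in the mediation models. An unlisted set of relevant covariates also leaves the choice open for each instrument until the data are in hand, in an aim for which the plan already accepts an inflated type 1 error.

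**Working it through.** **1. Reproduce the plan's figure.** The inputs come from the Power section: "All power analyses assume a significance level of 0.05 and a two-sided test"; 300 × 0.75 / 2 = 112.5, taken as 112 per group; a two-group t-test. With the noncentral t distribution, df = 2 × 112 − 2 = 222 and noncentrality 0.376 × √(112/2) = 2.81, power is 0.79999. Solving for 80% power gives 0.3760 SD. The stated figure is exact for an unadjusted comparison.

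**2. Which analyses name the baseline score.**

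| Analysis of MAPS on a mechanism | Visits | Covariates as written | Same-measure baseline score |
|---|---|---|---|
| Mixed model | 3, 6, 12, 18 | relevant ones, not listed | left open |
| Linear regression | 18 | list taken over from the abstinence model | not on the list |
| Mediation a path, main analysis | 3, 6 or 12 | includes baseline mediator | named |

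The minimization factors under Baseline Assessment and Randomization are not identical to the list in the analysis section (for example, language and income appear only in the latter). Neither contains a mechanism score. The 18-month comparison, which is the one powered, is therefore the one where baseline adjustment is neither named nor supplied by the main mediation analysis.

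**3. What adjustment would give at 18 months.** The documents give no correlation r between baseline and 18-month scores, so r is assumed. With the baseline score as a covariate, residual SD = SD × √(1 − r²) and df = 221. The detectable effect is then about 0.376 × √(1 − r²):

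- r = 0.3: 0.376 × √0.91 = 0.359 SD
- r = 0.5: 0.376 × √0.75 = 0.326 SD
- r = 0.7: 0.376 × √0.51 = 0.269 SD

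| Assumed r | Variance removed (r²) | Detectable effect, 80% power | Power at 0.376 SD | n per group for 0.376 SD, 80% power |
|---|---|---|---|---|
| none (plan) | 0 | 0.376 SD | 80.0% | 112 |
| 0.3 | 9% | 0.359 SD | 83.6% | 102 |
| 0.5 | 25% | 0.326 SD | 89.9% | 84 |
| 0.7 | 49% | 0.269 SD | 97.5% | 57 |

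The last column uses the normal approximation, which also returns 112 for the plan's case.

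**4. The mixed model, averaged over four visits.** Assume one correlation r among all visits, baseline included, and 112 per group throughout. In units of SD², the variance of a woman's four-visit mean is (1 + 3r)/4 without baseline and (1 + 3r)/4 − r² with it.

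- r = 0.3: 0.475 against 0.385; detectable effect 0.259 against 0.233 SD; variance down 19%.
- r = 0.5: 0.625 against 0.375; 0.297 against 0.230 SD; variance down 40%.
- r = 0.7: 0.775 against 0.285; 0.331 against 0.201 SD; variance down 63%.

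Equal correlation favours adjustment. If follow-ups correlate 0.6 with each other but only 0.4 with baseline, the reduction is 0.16 / 0.70, about 23%. With 0.7 and 0.5 it is 0.25 / 0.775, about 32%.

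**5. Limit of the comparison.** Steps 3 and 4 compare with an analysis that has no covariates. The planned regression already carries the listed ones. The gain over it depends on the correlation that remains between baseline and follow-up scores once those are accounted for, which the documents do not give either.

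**The case against.** The strongest reply is that the plan is largely sound here and merely terse. The mixed-model text does not confine its covariates to the minimization factors, and relevant covariates can be read to include a baseline score. The listed set was written for abstinence among current smokers, an outcome with no useful baseline value, and the sentence replacing logistic by linear regression changes the type of model without expressly freezing the list. The a path is itself an estimate of the MAPS effect on the mechanism; it adjusts for baseline, and a repeated-measures version is foreseen. Aim 2 is called quasi-exploratory, and the sample size was set for Aim 1.

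Most of this stands. It reduces the mixed-model part to an ambiguity and limits the importance of the whole. It does not supply the missing covariate at 18 months: the only list that the linear regression inherits contains no mechanism score, the main mediation analysis stops at month 12, and the visits of the repeated-measures version are not given.

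A reader might go further and infer that Aim 2 as a whole ignores baseline scores. The mediation text says otherwise. A reader might infer bias; randomization keeps the unadjusted contrast unbiased, and its standard error already reflects chance imbalance. A reader might also infer conflicting answers for one mechanism. At 18 months the main mediation analysis has no a-path estimate to conflict with, and at earlier visits a difference is only a possibility.

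**Conclusion.** The point holds in a limited form and is minor. For the 18-month regression, the baseline score of the mechanism is absent from the inherited covariate list. For the mixed model, its use is undecided. Both are gaps in precision and pre-specification. Neither shows that the stated power is wrong or that Aim 2 falls short of it: 0.376 SD is correct for the test described and takes no credit for baseline adjustment.

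Under correlations of 0.3 to 0.7, which are assumptions, the 18-month detectable effect would move from 0.376 to between about 0.36 and 0.27 SD relative to an unadjusted t-test. At the low end the benefit is small. The improvement over the planned covariate-adjusted model may be smaller and cannot be calculated from the documents. No conclusion about abstinence depends on it.

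**What to change.** In Data Analysis Approach, add one sentence: for each mechanism, the mixed model and the 18-month linear regression take post-baseline scores as the outcome and include the baseline score of the same measure as a covariate, alongside the minimization factors, as the a path already does. In the Aim 2 part of Power, label 0.376 SD as the unadjusted, conservative figure.

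The cost is a sentence and a label. Randomization follows completion of the baseline assessment, so the scores are already collected. Each model gains one covariate, and neither the sample size nor the visit schedule changes.

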Assessment calls will occur at Baseline and at 3, 6, 12, and 18 months after Baseline. The primary outcomes are abstinence from tobacco at the 18-month follow-up and abstinence across all follow-ups. Secondary outcomes are smoking quit attempts, cigarettes per day, use of the quitline, and cost-effectiveness. Participants will be scheduled to complete a baseline assessment call within one week. Following the baseline assessment, participants will be randomly assigned to ST or MAPS. Participants will schedule their first counseling call at that time (see Table 1).

Recruitment. Participants will be women with a diagnosis of cervical cancer or high grade cervical dysplasia who report smoking any cigarettes within the past 30 days, recruited through the Stephenson Cancer Center or OU Physicians at the University of Oklahoma Health Sciences Center, via the ClinicalTrials.gov website, by responding to recruitment flyers and internet advertisements (e.g., flyers in clinics, Facebook), and through referrals from healthcare providers.

Participant Eligibility. Inclusion criteria: ≥ 18 ; current smoker with a history of at least 100 lifetime cigarettes and a self-report of smoking within the last 30 days; history of cervical cancer or high grade cervical dysplasia (we have defined survivorship as beginning at the time of cancer diagnosis, consistent with the NCI definition); has a working cell phone; valid home address; speaks English, Spanish or both languages. Exclusion criteria: current use of tobacco cessation medications; self-report of being pregnant or lactating; or, another household member enrolled in the study; or contraindication of nicotine patch use unless under the supervision of a physician as advised by project staff.

Table 1. Schedule of Study Procedures and Assessments	Screening	Baseline	Month 3	Month 6	Month 12	Month 18
Inclusion/Exclusion Criteria	X	X				
Compensation		\$60	\$60	\$60	\$60	\$60
TREATMENT PROCEDURES						
Standard Treatment (ST)	Delivered at Baseline, and Months 6 and 12					
Motivation And Problem Solving (MAPS)	ST plus up to 6 MAPS Counseling Calls delivered over 12 months					
DEMOGRAPHICS, MENTAL HEALTH						
Demographics and Smoking History		X				
Cancer stage at diagnosis, time since diagnosis, current stage, treatment status	X					
Subjective Social Status		X	X	X	X	X
Fear of Cancer Recurrence Inventory (FCRI)	X	X	X	X	X	X
MOTIVATION						
Contemplation Ladder		X	X	X	X	X

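### Poisson regression is an allowed 18-month analysis of cigarettes per day with no allowance for overdispersion; naming robust standard errors is a minor, cheap improvement

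*Combined protocol and SAP*

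**What the plan says.** Cigarettes per day is a secondary outcome. Under Approach, Project Design and Procedures: "Secondary outcomes are smoking quit attempts, cigarettes per day, use of the quitline, and cost-effectiveness". Specific Aims also lists it as secondary.

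Statistical Considerations, Data Analysis Approach, treats it as a continuous measure. Across visits it is analysed by a linear mixed model, and at 18 months "the logistic regression analysis for the 18-month assessment will be replaced by multiple linear regression". On scale: "Normalizing transformations for continuous measures (such as cigarettes per day) will be applied as appropriate". Then comes the option at issue: "Alternatively, Poisson GLMM or Poisson regression could be used to analyze the effect of MAPS on cigarettes per day".

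No rule says when the Poisson option applies. Nothing in the statistical section mentions a dispersion check, a quasi-Poisson scale, a sandwich variance or a negative binomial model. The word robust occurs there once, under Missing Data and Dropouts, and refers to agreement between primary and sensitivity results.

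The covariates given for the 18-month logistic model are the "factors used in the minimization procedures (race/ethnicity, language, age, education, income, cigarettes/day, cervical cancer stage, and time since diagnosis". Baseline cigarettes per day is among them, so the check below adjusts for it.

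**The concern.** The default Poisson standard error takes the residual variance to equal the mean. Cigarettes per day is unlikely to meet that in this trial. Eligibility asks for some smoking in the last 30 days and 100 lifetime cigarettes, with no minimum daily rate, so a wide spread can be expected. The Power section plans for "abstinence rates of 10% and 21.9% in ST and MAPS respectively" at 18 months. If abstainers are entered as 0, they add a cluster of zeros that no Poisson distribution with a mean near 10 would produce. The documents do not say how abstainers enter.

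If the Poisson option is taken with default standard errors, intervals for the rate ratio are too narrow, and a chance difference between arms could be reported as a reduction in smoking.

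**Working it through.** **Reproducing the plan's figures.** The plan gives no mean, SD or error rate for cigarettes per day. The nearest figures supply the sample sizes and abstinence rates used here, and both reproduce:

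- 10% vs 21.9%, 150 per arm: z = (0.119·√150 − 1.96·√(2·0.1595·0.8405)) / √(0.10·0.90 + 0.219·0.781) = (1.457 − 1.015)/0.511 = 0.87, so power is 80.7%.
- 0.376 SD with "a sample size of 300 (112 per group at 18 months": 0.376·√(112/2) − 1.96 = 0.854, so power is 80.3% (80.0% by the noncentral t).

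**Inputs.** From the documents: alpha 0.05 two-sided; 150 per arm, or 112 after 25% attrition; zeros between 0 and 21.9%. Assumed: mean among smokers 8–15, SD 5–10, correlation with baseline 0.3–0.8.

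**Closed form.** Let φ be residual variance divided by the mean. A Wald test that uses the Poisson standard error has

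type I error = 2[1 − Φ(1.96/√φ)].

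This gives 5% at φ = 1, 10% at 1.42, 17% at 2, 26% at 3, 38% at 5 and 49% at 8.06. At a mean of 10, φ = 1.42 is a residual SD of √14.2 = 3.8. Sample size does not enter, so a larger trial does not cure the problem.

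With smoker mean m, SD s, zero fraction p₀, overall mean μ = (1−p₀)m and baseline correlation r,

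φ ≈ (1−r²)·[(1−p₀)(s²+m²) − μ²]/μ.

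Two examples:

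- m = 10, s = 5, p₀ = 0, r = 0.8: φ = 0.36·25/10 = 0.90; error 3.9%.
- m = 12, s = 8, p₀ = 0.10, r = 0.5: μ = 10.8; φ = 0.75·(0.9·208 − 116.64)/10.8 = 0.75·6.53 = 4.9; error 38%.

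**Simulation.** Null data: gamma counts rounded to integers, zeros assigned at random, adjusted for log baseline, 2,000 trials per row. Monte Carlo standard error is √(0.05·0.95/2000) = 0.5 points at 5% and √(0.4·0.6/2000) = 1.1 points at 40%.

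| Mean/SD | Zeros | r | Closed form | Poisson SE, 112 per arm | Poisson SE, 150 per arm | Robust SE, 112 / 150 |
|---|---|---|---|---|---|---|
| 10/5 | 0 | 0.8 | 3.9% | 4.4% | 4.4% | 5.4 / 5.1% |
| 10/5 | 0 | 0.5 | 15.2% | 16.6% | 14.4% | 5.2 / 4.0% |
| 12/8 | 0 | 0.7 | 23.5% | 23.6% | 25.2% | 6.1 / 5.2% |
| 10/5 | 10% | 0.7 | 14.2% | 20.9% | 20.3% | 5.1 / 4.3% |
| 12/6 | 10% | 0.7 | 18.1% | 24.4% | 25.4% | 6.0 / 5.6% |
| 12/8 | 10% | 0.5 | 37.6% | 40.6% | 40.8% | 5.1 / 5.2% |
| 15/10 | 10% | 0.5 | 42.8% | 44.0% | 45.6% | 4.4 / 4.3% |
| 15/10 | 20% | 0.3 | 50.9% | 54.2% | 53.1% | 4.8 / 5.1% |

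For the last row, φ = 0.91·(0.8·325 − 144)/12 = 8.80. The closed form runs low where there are zeros, because baseline does not predict who becomes a zero in the simulation.

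A separate simulation used mean/SD 10/6, 12/8 and 15/9, correlations 0.6 and 0.8, and 112 per arm. Poisson standard errors gave 10–30% without zeros and 22–47% with 10–21.9% zeros; robust standard errors gave 4–6%. In a further run on these three pairs, also at 150 per arm and with raw as well as log baseline, the robust standard error averaged 1.16 to 2.70 times the Poisson one, and linear regression held 4–6%.

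**The case against.** The strongest reply is that this is an option, not a commitment. The linear models are stated as what will be done; Poisson only could be used. The plan is silent on the variance estimator and does not prescribe the default one. Error arises only if Poisson is chosen, dispersion goes unchecked and the default standard error is reported. That stands, and it is why the point is minor. It does not remove the point: the named method, run as written, gives standard errors that are too small under most plausible inputs, and no rule fixes the choice in advance.

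Three stronger readings are tempting and should be resisted.

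- **A fixed range.** A reader might take about 10–49% as bounds on the error rate. The documents supply none of the inputs needed for bounds. The table runs from 4.4% to 54%, and with mean/SD 10/4, correlation 0.8 and no zeros the test is conservative, at under 2%. The top of the range needs abstainers entered as 0 and, for the three mean/SD pairs in the separate simulation, 21.9% zeros in both arms with no true effect. In the Power section 21.9% is the MAPS rate under the alternative; the planning rate for ST is 10%. At 10% zeros in both arms those pairs gave 22–38%. Table 2 lists ST rates up to 40%, so a higher zero fraction is possible, but it is not the planning null.
- **The Poisson GLMM.** A reader might extend the criticism to it. The plan describes its abstinence GLMM as one that will "parameterize them with blocking on individual nested within treatment conditions"; a subject-level term of that kind in the Poisson version would absorb between-person spread. The GLMM's error rates have not been established here, so none are claimed.
- **Dropping Poisson.** A reader might conclude that rate ratios should be demoted, or the GLMM replaced by GEE. The defect does not call for either. Unweighted GEE generally needs stronger missing-data assumptions than a correctly specified likelihood-based mixed model, which matters at the 25% attrition that the plan assumes for the mechanism analyses.

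**Conclusion.** The point holds as a cheap improvement of minor weight. It is confined to Poisson regression of cigarettes per day at 18 months with model-based standard errors. Against a nominal 5%, the error is:

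- about 4–5% only when small spread, no zeros and high baseline correlation coincide;
- about 10–30% with wider spread and no zeros;
- about 20–50% when 10–22% of participants enter as 0.

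All three figures are conditional on assumed means, SDs, correlations and zero coding. What does not depend on those inputs is the mechanism: inflation follows whenever residual variance exceeds the mean, and it passes 10% once the ratio is above 1.42. The linear analyses and the primary abstinence test are untouched.

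**What to change.** State that the linear model is the main analysis of cigarettes per day. Leave the sentence on transformations alone, since it also governs the mechanism measures. Keep the Poisson sentence, "Alternatively, Poisson GLMM or Poisson regression could be used to analyze the effect of MAPS on cigarettes per day", and append: *; Poisson regression at 18 months will use robust (sandwich) standard errors.*

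Robust errors are the better choice to name. They gave 4.0–6.1% across the scenarios of the tabulated simulation. A quasi-Poisson scale gave 4.1–6.8% there and up to 8.5% in other runs.

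The cost is one clause, with no new data or software. Rate-ratio intervals will be wider than plain Poisson intervals, by up to about 2.7 times under the assumed inputs. That width reflects the actual variability in the data.
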